### **Number of subjects**

The subjects are divided into two groups, 20 in each group.

### **Methods of drug administration**

Subjects with treatment-resistant depression who meet the inclusion criteria and do not meet the exclusion criteria are randomly assigned to the following two study groups:

Group 1: A (2 weeks) + C (4 weeks)

Group 2: B (2 weeks) + C (4 weeks)

A: Ethosuximide (capsule, 250mg/capsule)

B: Placebo (capsule, 250mg/capsule)

C: Escitalopram (tablet, 10mg/pill)

usage and dosage:

Drug A, 2 times/day, take it orally after breakfast/dinner; take 500mg in the morning and 500mg in the evening on day1, 500mg in the morning and 750mg in the evening on day2, 750mg in the morning and 750mg in the evening on day3, 750mg in the morning and 1000mg in the evening on day4, 1000mg in the morning and 1000mg in the evening on day5, maintain this dose until the end of treatment for 2 weeks.

The usage and dosage of Drug B are the same as above.

Drug C, 1 time/day, 20mg/day, take it orally after breakfast, take it for 4 weeks without interruption.

The time of the first administration should be after the next day's breakfast randomly. If the patient had taken escitalopram or was allergic to escitalopram in the past, the researchers would choose another appropriate antidepressant according to the patient's condition. Medication cycle: The study drugs will be taken for 6 weeks.

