### **Screening/Cleaning Period (Day-6 - 0) - Visit 0**

Visit will be conducted on day -6 to 0 (at least day -2 to 0) with the screening period ranging from 3 to 7 days. It will need to be re-screened if screening dates are more than 7 days from the date of administration. If antipsychotics, antidepressants and mood stabilizers were used before randomization, the cleaning time of these drugs should be more than 5 half-lives. Contents of visit:

1. Sign informed consents;
2. Collect demographic data: name, sex, birth date, nationality, height etc;
3. Inquiry about previous history;
4. Vital signs: at least including blood pressure (sitting position), heart rate,

respiratory rate, body temperature and weight;

5. Physical examination: at least including head face, skin system, lymph node, eye, ear, nose, throat, mouth, respiratory system, abdomen, cardiovascular system, musculoskeletal system and nervous system;

6. Diagnosis of major depressive disorder(single or recurrent episodes) is made according to DSM-V criteria;

7. Subjects with previous or current depressive episodes do not response to two different antidepressants with recommended doses and adequate duration (maximum treatment dose of at least 6 weeks);

8. Scale score: MADRS;

9. Laboratory tests:

complete blood count: hemoglobin (HGB), red blood cell count (RBC), white blood cell count (WBC), neutrophil count (NEUT), lymphocyte count (LY), platelet count (PLT);

routine urine: PH, white blood cells, erythrocyte (ERY), nitrite (NIT), protein, glucose (GLU), ketone body (KET), urinary cholanogen (UBG), bilirubin;

blood biochemical examination: aspartate aminotransferase (AST), glutamate aminotransferase, alkaline phosphatase (ALP), glutamyl transpeptidase (GGT), lactate dehydrogenase (LD), total protein, albumin (ALB), urea nitrogen (BUN), creatinine, creatine kinase (CK), total bilirubin (TBIL), direct bilirubin (DBIL), uric acid, blood sugar (Glu), triglyceride (TG), total cholesterol (TC), high density lipoprotein (HDL) ,low density lipoprotein (LDL), sodium (Na), potassium (K), chlorine, phosphorus (P), calcium (Ca), prolactin (PRL);

pregnancy test: detection of HCG in blood or urine of women with childbearing age;

thyroid function examination: FT3, FT4, TT3, TT4, TSH;

10. ECG: 12 leads cardiogram;

11. Inclusion and exclusion criteria;

12. Records of combined medication.

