### **Baseline period (day 1) - Visit 1**

The baseline period is day1.

Contents of visit:

1. Inclusion and exclusion criteria;
2. Diagnosis of major depressive disorder(single or recurrent episodes) is made according to DSM-V criteria;
3. Subjects with previous or current depressive episodes do not response to two different antidepressants with recommended doses and adequate duration (maximum treatment dose of at least 6 weeks);
4. Scale score: MADRS、 QIDS-SR、 HAMA、 YMRS;
5. Vital signs: including blood pressure (sitting position), heart rate, respiratory rate, body temperature and weight;
6. Physical examination: including head face, skin system, lymph node, eye, ear, nose, throat, mouth, respiratory system, abdomen, cardiovascular system, musculoskeletal system and nervous system;
7. Records of adverse events;
8. Records of combined medication;
9. Randomization;
10. Drugs dispensing.

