### **Treatment Period (Day 2) - Visit 2**

Visit will be conducted on day2 after randomization(24 hours after taking medicine).

Contents of visit:

1. Scale score: MADRS、 QIDS-SR、 HAMA、 YMRS;
2. Vital signs: including blood pressure (sitting position), heart rate, respiratory rate, body temperature and weight;
3. Records of adverse event;
4. Records of combined medication;
5. Drugs recovery and dispensing.

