### **Treatment Period (Day 3) - Visit 3**

Visit will be conducted on day3 after randomization(48 hours after taking medicine).

Contents of visit:

1. Scale score: MADRS、 QIDS-SR、 HAMA、 YMRS;
2. Vital signs: including blood pressure (sitting position), heart rate, respiratory rate, body temperature and weight;
3. Records of adverse event;
4. Records of combined medication;
5. Drugs recovery and dispensing.

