#### **Treatment Period (Day 4) - Visit 4**

Visit will be conducted on day4 after randomization(72 hours after taking medicine).

Contents of visit:

1. Laboratory tests: blood concentration of ethambutamine;
2. Scale score: MADRS、 QIDS-SR、 HAMA、 YMRS;
3. Vital signs: including blood pressure (sitting position), heart rate, respiratory rate, body temperature and weight;
4. Records of adverse events;
5. Records of combined medication;
6. Drug recovery and dispensing;

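### The first-dose sentence does not fit the study-day calendar: followed together with the visit-day headings, it puts ratings labelled 24, 48 and 72 hours at about 0, 24 and 48 hours

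*Protocol*

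**What the plan says.** Four parts of the protocol bear on when the first dose falls.

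- **First dose.** Methods of drug administration states: "The time of the first administration should be after the next day's breakfast randomly".
- **Baseline.** The Visit 1 section states "The baseline period is day1". Its list of contents includes "9. Randomization", followed by drug dispensing.
- **Early visits.** Visit 2: "Visit will be conducted on day2 after randomization(24 hours after taking medicine". Visit 3: "Visit will be conducted on day3 after randomization(48 hours after taking medicine". Visit 4: "Visit will be conducted on day4 after randomization(72 hours after taking medicine". The headings of these sections carry Days 2, 3 and 4.
- **Screening limit.** The screening section allows Day -6 to Day 0 and adds: "It will need to be re-screened if screening dates are more than 7 days from the date of administration".

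The titration begins "take 500mg in the morning and 500mg in the evening on day1, 500mg in the morning and 750mg in the evening on day2". It does not say whether its first day is study Day 1 or the first day of dosing. SAP section 2.1 repeats the titration but defines neither the study day of the first dose nor time since dosing.

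**The concern.** With randomisation on Day 1, a first dose on the following morning falls on Day 2. A rating 24 hours after dosing cannot then fall on Day 2. One of three statements has to give way: the next-day sentence, the placing of randomisation on Day 1, or the use of one day count for visits and baseline.

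The introduction argues for a rapid antidepressant effect, and the three daily ratings at Visits 2 to 4 are where such an effect would first show. They also enter the main analysis. The main efficacy measure is MADRS change at the treatment visits, with no single time point named (Protocol, Main efficacy measures; SAP 3.1.1), and SAP 5.4 analyses the scale time points by repeated-measures ANOVA. Visits 2 to 4 are three of the nine post-baseline ratings. If staff followed both the next-day sentence and the day headings, the score reported as 24 hours would be taken before, or within hours of, the first dose.

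**Working it through.** **Inputs.** Randomisation is on Day 1 (Visit 1). Visits 2, 3 and 4 are on Days 2, 3 and 4 (section headings). Daily totals from the titration are 1000, 1250, 1500, 1750 and then 2000 mg (Methods of drug administration). Screening runs from Day -6, with a 7-day limit to dosing (screening section). The first phase lasts 2 weeks.

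**Hours since first dose** = 24 × (visit day − first-dose day), assuming that ratings are made at the clock time of the first dose.

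The plan's own figures, with a first dose on Day 1: 24 × (2 − 1) = 24; 24 × (3 − 1) = 48; 24 × (4 − 1) = 72. The labels are reproduced.

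With a first dose on Day 2: 24 × (2 − 2) = 0; 24 × (3 − 2) = 24; 24 × (4 − 2) = 48. Each is 24 hours short of its label.

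**Readings tried**

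| Reading | Hours at Visits 2, 3, 4 | What has to give way |
|---|---|---|
| A. Randomised Day 1, first dose Day 2, visits on the headed days | 0, 24, 48 | The hour labels |
| B. Randomised and first dosed on Day 1 | 24, 48, 72 | The next-day sentence |
| C. Randomised Day 0, first dose Day 1 | 24, 48, 72 | Randomisation listed under Day 1 |
| D. Randomised Day 1, first dose Day 2, visits 2, 3 and 4 elapsed days after randomisation | 24, 48, 72 | The headings: visits move to Days 3, 4 and 5 when baseline is Day 1 |

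No reading keeps every statement.

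**Scheduled drug taken before each visit**, summing whole dosing days up to the day before:

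| Visit day | First dose Day 1 | First dose Day 2 |
|---|---|---|
| 2 | 1000 mg | 0 mg |
| 3 | 1000 + 1250 = 2250 mg | 1000 mg |
| 4 | 2250 + 1500 = 3750 mg | 2250 mg |
| 6 | 3750 + 1750 + 2000 = 7500 mg | 3750 + 1750 = 5500 mg |

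The zero assumes a rating before that morning's dose. A rating after it would follow 500 mg. The Day 6 row also affects the blood sample due then: Day 6 is the second day at 2000 mg with a Day 1 start and the first with a Day 2 start.

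**End of a 14-day first phase** = first-dose day + 13. A Day 1 start gives Day 14, the day of Visit 7. A Day 2 start gives Day 15, one day after it.

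**Screening interval from Day -6** = first-dose day + 6. A Day 1 start gives 7 days, just inside the limit. A Day 2 start gives 8 days, which triggers re-screening for a patient screened on the earliest permitted day.

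**The case against.** The strongest reply is that the problem is one badly translated sentence. Its last word makes no literal sense where it stands, so a next-day rule is an interpretation. The sentence follows the escitalopram dosing line and precedes the escitalopram substitution rule, so it could concern the first escitalopram dose. Several other statements agree with a Day 1 first dose: the three hour labels, the Day 14 visit and the 7-day limit. The Visit 2 to 4 sections already define those ratings by time after taking medicine, so staff who follow that text would not rate before dosing. The titration's first day may simply be the first day of dosing, so that table need not conflict with anything. The protocol defers to a flow chart that is not visible in the text reviewed and may settle the question.

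Most of this stands, and it limits the point to an unresolved conflict in wording. It does not remove the conflict. The sentence names no drug, and the day after randomisation remains its most natural sense. A Day 1 morning dose would also need the baseline ratings, randomisation and dispensing to be finished in time for it, which the protocol does not address. A clear flow chart would still leave the written sections in disagreement.

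A reader might go further and infer that the comparison between arms is biased. The documents do not support that: both arms have the same visit and dosing schedule under double blinding, so any shift is common to both. A reader might also infer that patients will be timed differently from one another. That is possible if staff read the text differently, but nothing in the documents shows it, and the trial is a single-centre study of 40 inpatients.

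**Conclusion.** The conflict is real and minor. If the next-day sentence and the day headings are both followed, Visits 2, 3 and 4 fall about 0, 24 and 48 hours after the first dose, against labels of 24, 48 and 72. The first phase then outlasts the Day 14 visit by one day, and the earliest screening day exceeds the limit by one day.

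The consequence would be a mislabelled time of onset and possibly diluted contrasts at the earliest visits, without bias in the randomised comparison. The effect on MADRS cannot be sized, because the documents give no effect size or standard deviation.

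The conclusion rests on three assumptions: that the garbled sentence refers to the day after randomisation, that it concerns the first study capsule, and that ratings are made at about the clock time of the first dose. The documents do not support a flat statement that the first dose is set for Day 2, or that the 24-hour score is certainly a pre-dose score.

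**What to change.** - Reconcile Methods of drug administration with the screening section and the Visit 1 to 10 sections, using one definition of Day 1 and one statement of the study day of the first dose. Which day is right is for the sponsor to say.
- Say whether the titration's days are study days or dosing days, and which drug the first-dose sentence concerns.
- Keep Visits 2 to 4 anchored to hours from the recorded first dose. Apply the same clock to the blood samples, the Day 14 visit and the 7-day screening limit, and check the flow chart against it.
- Record the date and time of the first dose and of each early rating, if the case report form does not already do so.
- In the SAP, report the early visits by hours since first dose.

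The cost is a wording amendment, at most a few date and time fields, and a sentence in the SAP. No visit is added.

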### **Random double-blind method**

### Random method

Random tables and random codes are generated by SAS software. Each subject would get a unique random code according to the random tables, and every random code corresponds to the corresponding study group and drug number. Each participant has the same opportunity to be assigned to the study or the control group.(the ratio of the number of cases between the study group and the control group is 1:1)

### Double-blind method

It is a double-blind and double-simulation study. All subjects, researchers and evaluators are blind to grouping information in the course of the clinical study. The results of the study are audited by blind state data. The placebos are administered in capsules with no difference in appearance, color, weight or odor from the positive drugs. Both subjects and drugs are coded blindly.

In the study, the coding system for research drugs have an emergency blindness detection procedure, so as to quickly identify the drugs in emergency medical condition, without destroying the blind design of clinical research.

### **Research visit**

Participants must read and sign the informed consents that are approved by the Ethics Committee(EC) before starting the study. Checks and research procedures are carried out according to the research flow chat.

### **Screening/Cleaning Period (Day-6 - 0) - Visit 0**

Visit will be conducted on day -6 to 0 (at least day -2 to 0) with the screening period ranging from 3 to 7 days. It will need to be re-screened if screening dates are more than 7 days from the date of administration. If antipsychotics, antidepressants and mood stabilizers were used before randomization, the cleaning time of these drugs should be more than 5 half-lives. Contents of visit:

1. Sign informed consents;
2. Collect demographic data: name, sex, birth date, nationality, height etc;
3. Inquiry about previous history;
4. Vital signs: at least including blood pressure (sitting position), heart rate,

respiratory rate, body temperature and weight;

5. Physical examination: at least including head face, skin system, lymph node, eye, ear, nose, throat, mouth, respiratory system, abdomen, cardiovascular system, musculoskeletal system and nervous system;

6. Diagnosis of major depressive disorder(single or recurrent episodes) is made according to DSM-V criteria;

7. Subjects with previous or current depressive episodes do not response to two different antidepressants with recommended doses and adequate duration (maximum treatment dose of at least 6 weeks);

8. Scale score: MADRS;

9. Laboratory tests:

complete blood count: hemoglobin (HGB), red blood cell count (RBC), white blood cell count (WBC), neutrophil count (NEUT), lymphocyte count (LY), platelet count (PLT);

routine urine: PH, white blood cells, erythrocyte (ERY), nitrite (NIT), protein, glucose (GLU), ketone body (KET), urinary cholanogen (UBG), bilirubin;

blood biochemical examination: aspartate aminotransferase (AST), glutamate aminotransferase, alkaline phosphatase (ALP), glutamyl transpeptidase (GGT), lactate dehydrogenase (LD), total protein, albumin (ALB), urea nitrogen (BUN), creatinine, creatine kinase (CK), total bilirubin (TBIL), direct bilirubin (DBIL), uric acid, blood sugar (Glu), triglyceride (TG), total cholesterol (TC), high density lipoprotein (HDL) ,low density lipoprotein (LDL), sodium (Na), potassium (K), chlorine, phosphorus (P), calcium (Ca), prolactin (PRL);

pregnancy test: detection of HCG in blood or urine of women with childbearing age;

thyroid function examination: FT3, FT4, TT3, TT4, TSH;

10. ECG: 12 leads cardiogram;

11. Inclusion and exclusion criteria;

12. Records of combined medication.

### **Baseline period (day 1) - Visit 1**

The baseline period is day1.

Contents of visit:

1. Inclusion and exclusion criteria;
2. Diagnosis of major depressive disorder(single or recurrent episodes) is made according to DSM-V criteria;
3. Subjects with previous or current depressive episodes do not response to two different antidepressants with recommended doses and adequate duration (maximum treatment dose of at least 6 weeks);
4. Scale score: MADRS、 QIDS-SR、 HAMA、 YMRS;
5. Vital signs: including blood pressure (sitting position), heart rate, respiratory rate, body temperature and weight;
6. Physical examination: including head face, skin system, lymph node, eye, ear, nose, throat, mouth, respiratory system, abdomen, cardiovascular system, musculoskeletal system and nervous system;
7. Records of adverse events;
8. Records of combined medication;
9. Randomization;
10. Drugs dispensing.

### **Treatment Period (Day 2) - Visit 2**

Visit will be conducted on day2 after randomization(24 hours after taking medicine).

Contents of visit:

1. Scale score: MADRS、 QIDS-SR、 HAMA、 YMRS;
2. Vital signs: including blood pressure (sitting position), heart rate, respiratory rate, body temperature and weight;
3. Records of adverse event;
4. Records of combined medication;
5. Drugs recovery and dispensing.

### **Treatment Period (Day 3) - Visit 3**

Visit will be conducted on day3 after randomization(48 hours after taking medicine).

Contents of visit:

1. Scale score: MADRS、 QIDS-SR、 HAMA、 YMRS;
2. Vital signs: including blood pressure (sitting position), heart rate, respiratory rate, body temperature and weight;
3. Records of adverse event;
4. Records of combined medication;
5. Drugs recovery and dispensing.

#### **Treatment Period (Day 4) - Visit 4**

Visit will be conducted on day4 after randomization(72 hours after taking medicine).

Contents of visit:

1. Laboratory tests: blood concentration of ethambutamine;
2. Scale score: MADRS、 QIDS-SR、 HAMA、 YMRS;
3. Vital signs: including blood pressure (sitting position), heart rate, respiratory rate, body temperature and weight;
4. Records of adverse events;
5. Records of combined medication;
6. Drug recovery and dispensing;

#### **Treatment Period (Day 6) - Visit 5**

Visit will be conducted on day6 after randomization.

Contents of visit:

1. Laboratory tests: blood concentration of ethambutamine;
2. Scale score: MADRS、 QIDS-SR、 HAMA、 YMRS;
3. Vital signs: including blood pressure (sitting position), heart rate, respiratory rate, body temperature and weight;
4. Records of adverse events;
5. Records of combined medication;
6. Drugs recovery and dispensing.

### **Treatment Period (Day 10) - Visit 6**

Visit will be conducted on day10 after randomization.

Contents of visit:

1. Laboratory tests: blood concentration of ethambutamine;
2. Scale score: MADRS、 QIDS-SR、 HAMA、 YMRS;
3. Vital signs: including blood pressure (sitting position), heart rate, respiratory rate, body temperature and weight;
4. Records of adverse events;
5. Records of combined medication;
6. Drugs recovery and dispensing.

### **Treatment Period (Day 14) - Visit 7**

Visit will be conducted on day14 after randomization.

Contents of visit:

1. Scale score: MADRS、 QIDS-SR、 HAMA、 YMRS;
2. Laboratory tests:
  - blood concentration of ethambutamine.
  - complete blood count: hemoglobin (HGB), red blood cell count (RBC), white blood cell count (WBC), neutrophil count (NEUT), lymphocyte count (LY), platelet count (PLT);
  - routine urine: PH, white blood cells, erythrocyte (ERY), nitrite (NIT), protein, glucose (GLU), ketone body (KET), urinary cholanogen (UBG), bilirubin;
  - blood biochemical examination: aspartate aminotransferase (AST), glutamate aminotransferase, alkaline phosphatase (ALP), glutamyl transpeptidase (GGT), lactate dehydrogenase (LD), total protein, albumin (ALB), urea nitrogen (BUN), creatinine, creatine kinase (CK), total bilirubin (TBIL), direct bilirubin (DBIL), uric acid, blood sugar (Glu), triglyceride (TG), total cholesterol (TC), high density lipoprotein (HDL) ,low density lipoprotein (LDL), sodium (Na), potassium (K), chlorine, phosphorus (P), calcium (Ca), prolactin (PRL);
3. ECG: 12 leads cardiogram;

4. Vital signs: including blood pressure (sitting position), heart rate, respiratory rate, body temperature and weight;
5. Records of adverse events;
6. Records of combined medication;
7. Drugs recovery and dispensing;

#### **Treatment Period (Day 22±1) - Visit 8**

Visit will be conducted on day22±1 after randomization.

Contents of visit:

1. Scale score: MADRS、 QIDS-SR、 HAMA、 YMRS;
2. Vital signs: including blood pressure (sitting position), heart rate, respiratory rate, body temperature and weight;
3. Records of adverse events;
4. Records of combined medication;
5. Drugs recovery and dispensing.

#### **Treatment Period (Day 29±1) - Visit 9**

Visit will be conducted on day29±1 after randomization.

Contents of visit:

1. Scale score: MADRS、 QIDS-SR、 HAMA、 YMRS;
2. Vital signs: including blood pressure (sitting position), heart rate, respiratory rate, body temperature and weight;
3. Records of adverse events;
4. Records of combined medication;
5. Drugs recovery and dispensing.

#### **Treatment Period (Day 42±1) - Visit 10**

Visit will be conducted on day42±1 after randomization.

Contents of visit:

1. Scale score: MADRS、 QIDS-SR、 HAMA、 YMRS;
2. Laboratory tests:  
blood concentration of ethambutamine.

complete blood count: hemoglobin (HGB), red blood cell count (RBC), white blood cell count (WBC), neutrophil count (NEUT), lymphocyte count (LY), platelet count (PLT);

routine urine: PH, white blood cells, erythrocyte (ERY), nitrite (NIT), protein, glucose (GLU), ketone body (KET), urinary cholanogen (UBG), bilirubin;

blood biochemical examination: aspartate aminotransferase (AST), glutamate aminotransferase, alkaline phosphatase (ALP), glutamyl transpeptidase (GGT), lactate dehydrogenase (LD), total protein, albumin (ALB), urea nitrogen (BUN), creatinine, creatine kinase (CK), total bilirubin (TBIL), direct bilirubin (DBIL), uric acid, blood sugar (Glu), triglyceride (TG), total cholesterol (TC), high density lipoprotein (HDL), low density lipoprotein (LDL), sodium (Na), potassium (K), chlorine, phosphorus (P), calcium (Ca), prolactin (PRL);

3. ECG: 12 leads cardiogram;
4. Vital signs: including blood pressure (sitting position), heart rate, respiratory rate, body temperature and weight;
5. Records of adverse events;
6. Records of combined medication.

